### B3. DESCRIPTION OF RESEARCH PROTOCOL

#### A. Study Design – Overview, Methods, Procedures

##### Study Design and plan:

The design of this study is a single center, single-blinded clinical research treatment study. This clinical study will be conducted at Beth Israel Deaconess Medical Center in Boston (the study was previously conducted at MGH and is currently being conducted at both institutions through Cede Review with MGH as the overseeing IRB and BIDMC). All subjects with a signed informed consent will be screened to ensure they meet all inclusion criteria and do not meet the exclusion criteria. After enrolment, the duration of the study is approximately 8 weeks, involving 3 or 4 visits. A schematic overview of the main procedures during each visit is illustrated in Appendix 2.

The clinical effect of the hypertonic saline treatment will be evaluated with Physician and patients Assessments at week 2 (t=2), week four (t=4) and week 8 (t=8) and compared with the first visit (baseline) (t=0). If necessary, subjects will be eligible to receive another hypertonic saline injected in week 2 and/or week 4, with a maximum of three injections. Simultaneously improvement will be assessed by ultrasound if possible, using the Philips Lumify Ultrasound Device, and by patients using HS Improvement Assessments. Pain and stinging during treatment sessions will be monitored using numeric rating scales (NRS). For monitoring quality of life the DLQI will be used.

Prior to performing any study related procedures, the investigator will discuss with each subject the nature of the study, its requirements and its restrictions. A written informed consent form will be obtained from each participant prior to any procedure. Each subject with a signed informed consent form will be screened at the first visit, to ensure all the inclusion criteria are met and none of the exclusion criteria. Medical history and demographic information will be taken. Patients will have their medication reviewed and undergo a full HS examination, including lesion counts, Hurley staging and target site assessment. Target HS area(s) will be digitally photographed and be imaged with ultrasound. The duration of the study is approximately 8 weeks, involving a minimum of 3 and a maximum of 4 visits. In case of an adverse event or disease progression, patients are instructed to call and/or visit the clinic. An overview of the exact procedures during each visit can be found in the chart

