**B. Statistical Considerations**

**a. Sample Size Justification:**

The total number of subjects to be studied is 20 and the number to be studied at BIDMC is 14. A sample size calculation is not applicable, for this is an early feasibility and tolerability pilot study.

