**b. Data Analysis:**

**Primary study parameter(s)**

The clinical efficacy will be measured by Physician and patients Assessments. These are continuous variables and depending on the date distribution a one way ANOVA, a Kruskal Wallis or a Wilcoxon rank sum test will be performed for analysis.

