**Secondary study parameter(s)**

Hence the small patient group in this pilot study, no power is expected from statistical analysis. Therefore all outcomes will be assessed by using descriptive statistics.

The clinical efficacy will also be measured using the following outcomes:

- Measuring the length and the lumen of the fistulas using ultrasound if possible. Since this variable is highly dependent on investigator and experience with ultrasound, descriptive statistics will be used to present this variable.

The patient reported outcomes:

- HS Improvement assessment: this is a continuous variable and depending on the date

distribution a one way ANOVA, a Kruskal Wallis or a Wilcoxon rank sum test will be performed for analysis.

- NRS to assess pain and stinging: continuous variable. Per individual a percentage improvement will be calculated as a main outcome.
- DLQI: continuous variable. this is a continuous variable and depending on the date distribution a one way ANOVA, a Kruskal Wallis or a Wilcoxon rank sum test will be performed for analysis.

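### The primary Assessments, HS Improvement and DLQI are given independent-group tests although the comparison is each patient with their own baseline, and the plan also says outcomes are descriptive only

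*Combined protocol and SAP*

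**What the plan says.** Section B3.A (Study Design and plan) describes a single treated group. The Physician and patients Assessments are made at weeks 2, 4 and 8, "and compared with the first visit (baseline) (t=0". No control arm, randomisation or other between-group comparison appears anywhere.

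Section B3.B.b, Primary study parameter(s), calls these assessments continuous and says that "depending on the date distribution a one way ANOVA, a Kruskal Wallis or a Wilcoxon rank sum test will be performed for analysis". It names no contrast and no time point.

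Under Secondary study parameter(s) the same three tests return for two more outcomes: "HS Improvement assessment: this is a continuous variable and depending on the date" distribution, and "DLQI: continuous variable. this is a continuous variable and depending on the date" distribution. The same section opens by saying that "no power is expected from statistical analysis" and continues "Therefore all outcomes will be assessed by using descriptive statistics".

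Two outcomes are outside this point. Ultrasound measurements are to be summarised descriptively. For the pain and stinging NRS, "Per individual a percentage improvement will be calculated as a main outcome", which is already a within-patient measure.

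**The concern.** One-way ANOVA, Kruskal-Wallis and the Wilcoxon rank-sum test all treat the groups being compared as different, independent people. Here the groups can only be visits of the same people. No paired or repeated-measures method is named for these outcomes. This does not look like a slip of the pen, since the wording occurs three times and all three tests are of the unpaired kind.

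The shape of the data cannot settle the choice either. It may decide between ANOVA and Kruskal-Wallis. Choosing between Kruskal-Wallis and the rank-sum test depends on how many groups are compared, which the plan does not say.

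If visits correlate positively, the tests are conservative. False positives are not inflated, but a real change may be missed and the reported precision is worse than the data support. The plan also leaves an analyst unsure whether to test at all. Section B10 says dissemination may include journal publication, so these p-values could be reported.

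**Working it through.** **Inputs from the plan.** 20 subjects in total (Sample Size Justification); visits at baseline and weeks 2, 4 and 8 (Study Design and plan). The plan states no alpha, SD, effect size, correlation or power, so it has no figure of its own to reproduce.

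**Assumed.** Two-sided 5% level, normal data, the same SD at each visit, the same correlation ρ between any two visits, 20 complete patients with one value each, ρ from 0 to 0.8, and a raw change of 0.65 or 0.8 SD.

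**Step 1: precision of the mean change.** The true variance is 2σ²(1−ρ)/n. An independent-group calculation uses 2σ²/n, so its standard error is too large by a factor 1/√(1−ρ), which is 1.41 at ρ = 0.5. The 95% CI half-widths are:
- visits treated as independent: t(38) × √(2/20) = 2.024 × 0.316 = 0.64 SD, whatever ρ is;
- paired, at ρ = 0.5: t(19) × √(2 × 0.5/20) = 2.093 × 0.224 = 0.47 SD.

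**Step 2: type I error, normal approximation.** The true level of an unpaired z-test is 2[1 − Φ(1.96/√(1−ρ))]:
- ρ = 0.3: 1.96/√0.7 = 2.34, giving 1.9%;
- ρ = 0.5: 1.96/√0.5 = 2.77, giving 0.6%;
- ρ = 0.7: 1.96/√0.3 = 3.58, giving 0.04%.

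**Step 3: simulation, baseline against one later visit** (20,000 trials per setting). Power is shown as rank-sum / signed-rank. The last column repeats the paired formula of step 1.

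| ρ | Rank-sum type I error | Power, 0.65 SD | Power, 0.8 SD | Paired CI half-width (SD) |
|---|---|---|---|---|
| 0 | 4.9% | 0.49 / 0.48 | 0.67 / 0.65 | 0.66 |
| 0.3 | 2.1% | 0.50 / 0.62 | 0.70 / 0.79 | 0.55 |
| 0.5 | 0.8% | 0.49 / 0.76 | 0.73 / 0.91 | 0.47 |
| 0.7 | 0.15% | 0.51 / 0.93 | 0.77 / 0.99 | 0.36 |
| 0.8 | 0.02% | 0.52 / 0.99 | 0.81 / 1.00 | 0.30 |

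A separate run of 60,000 trials with another seed gave rank-sum type I errors of 4.9%, 2.2%, 0.9%, 0.15% and 0.03%. At ρ = 0.5 the relative loss of power is (0.76 − 0.49)/0.76 = 36% for a 0.65 SD change and (0.91 − 0.73)/0.91 = 20% for 0.8 SD.

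**Step 4: all four visits compared.** Type I error of one-way ANOVA or Kruskal-Wallis is about 1.2% to 1.4% at ρ = 0.3, 0.3% at 0.5, and 0.02% to 0.03% at 0.7. In a run of 3,000 trials with ρ = 0.5 and a change building up to 0.5 SD at week 8, power was 0.11 for ANOVA against 0.44 for repeated-measures ANOVA, and 0.10 for Kruskal-Wallis against 0.35 for Friedman.

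**Step 5: where the direction fails.** At ρ = −0.3 (3,000 trials) the unpaired tests were too liberal: 8% for rank-sum and 10% for ANOVA and Kruskal-Wallis. The conservative direction therefore needs positive correlation. It also holds on average rather than in every dataset: at ρ = 0.5 with a 0.5 SD change, the unpaired p-value exceeded the paired one in 87% to 100% of runs, depending on the test.

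**Step 6: the two statements on testing.** The descriptive-only sentence and the tests for HS Improvement and DLQI stand under the same heading, Secondary study parameter(s). They cannot both be followed.

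**The case against.** The strongest reply is that little depends on these tests. The plan gives no sample size calculation, "for this is an early feasibility and tolerability pilot study", and it expects no power. No success criterion or go/no-go rule uses a p-value. The likely result is an over-cautious exploratory p-value, and pairing can be restored at analysis. This stands, and it limits the severity. It does not make the named tests suit the design.

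Other objections narrow the point:
- The descriptive-only sentence sits under the secondary heading and may mean secondary outcomes only. The contradiction is then certain for HS Improvement and DLQI, and reaches the primary Assessments only on the wider reading.
- The baseline comparison is tied explicitly only to the Physician and patients Assessments. For DLQI it is a reasonable inference, since no other contrast is given. HS Improvement may be a rating of change with no baseline value, in which case the repeated values are those after baseline and the fix must allow for it.
- Groups could be formed by institution or number of injections, but no such comparison is described.
- Patients may have several fistulas or target areas, and the plan does not say whether scoring is per patient or per site. Pooling sites as if independent could change the direction of the error. The figures assume one value per patient.
- Every magnitude rests on assumed inputs and complete data, while the plan allows three or four visits. The figures show a range and are not a forecast.

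**Conclusion.** The concern holds. For the primary Assessments, and by inference for DLQI and HS Improvement, the plan prescribes tests for independent groups where the only described comparison is within patients. With one value per patient and positive correlation between visits, the error is conservative. For ρ between 0.3 and 0.8 the rank-sum test's true level falls from 2.1% to 0.02%, and its power for a 0.65 SD change stays near 0.5 while the signed-rank test reaches 0.62 to 0.99. At ρ = 0 there is no loss. These figures assume normal data, equal SDs, 20 complete patients and a two-sided 5% level, none of which the documents supply. Separately, the plan contradicts itself on whether the secondary outcomes are tested. This should be fixed before analysis, but it does not threaten a pilot of this kind.

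**What to change.** Choose one of two routes and apply it in both Primary and Secondary study parameter(s).

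1. **Keep an exploratory test.** For the primary Assessments and DLQI, replace the three-test wording with one named analysis: change from baseline to week 8, the last listed assessment (the sponsor to confirm the time point), by Wilcoxon signed-rank test, with the Hodges-Lehmann estimate of the median change and its 95% CI, labelled exploratory. Report weeks 2 and 4 descriptively. Any analysis of all visits is supportive and uses a mixed model with patient as a random effect. If an outcome such as HS Improvement is scored as improvement since baseline, apply the same test and interval to the week-8 score against the no-change value. Amend the descriptive-only sentence to except these exploratory tests.
2. **Stay descriptive.** Delete the tests for all three outcomes and report within-patient change with a 95% CI.

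Under either route, state that each patient contributes one value per visit, or how several sites are combined.

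The cost is rewording three test statements and one sentence, plus this clarification. No extra patients, visits or data are needed.

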**Secondary study parameter(s)**

Hence the small patient group in this pilot study, no power is expected from statistical analysis. Therefore all outcomes will be assessed by using descriptive statistics.

The clinical efficacy will also be measured using the following outcomes:

- Measuring the length and the lumen of the fistulas using ultrasound if possible. Since this variable is highly dependent on investigator and experience with ultrasound, descriptive statistics will be used to present this variable.

The patient reported outcomes:

- HS Improvement assessment: this is a continuous variable and depending on the date

distribution a one way ANOVA, a Kruskal Wallis or a Wilcoxon rank sum test will be performed for analysis.

- NRS to assess pain and stinging: continuous variable. Per individual a percentage improvement will be calculated as a main outcome.
- DLQI: continuous variable. this is a continuous variable and depending on the date distribution a one way ANOVA, a Kruskal Wallis or a Wilcoxon rank sum test will be performed for analysis.

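### The secondary analysis section makes all outcomes descriptive yet prescribes independent-group tests for HS Improvement and DLQI, and these tests do not suit same-patient comparisons with baseline

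*Combined protocol and SAP*

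**What the plan says.** All references are to the combined protocol and SAP.

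- **Sample Size Justification (B3.B.a):** 20 subjects in total, 14 of them at BIDMC. No calculation is given, because "this is an early feasibility and tolerability pilot study".
- **Secondary study parameter(s) (B3.B.b), opening:** because the group is small, "no power is expected from statistical analysis". The next sentence is "Therefore all outcomes will be assessed by using descriptive statistics".
- **Same section, HS Improvement:** "HS Improvement assessment: this is a continuous variable and depending on the date". The sentence goes on to a choice among one-way ANOVA, Kruskal-Wallis and Wilcoxon rank sum, stated as a firm plan.
- **Same section, DLQI:** "DLQI: continuous variable. this is a continuous variable and depending on the date distribution a one way ANOVA", followed by the same two alternatives.
- **Same section, the other two outcomes:** ultrasound length and lumen are descriptive only, because they depend on the operator. NRS pain and stinging is an individual percentage improvement with no test named.
- **Primary study parameter(s) (B3.B.b):** for the physician and patient assessments, "These are continuous variables and depending on the date distribution a one way ANOVA, a Kruskal Wallis or a Wilcoxon rank sum test".
- **Study Design and plan (B3.A):** effect is judged by "Physician and patients Assessments at week 2 (t=2), week four (t=4) and week 8 (t=8"), each "compared with the first visit (baseline) (t=0"). No second treatment group is described.

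**The concern.** An analyst working from this text cannot tell whether HS Improvement and DLQI should get a p-value. The opening sentence rules p-values out, and the individual entries require them. The plan foresees abstracts and journal submission, and Dissemination of Research Results (B10) says the investigators are not primarily responsible for the analysis. The choice may therefore fall to someone with only this wording to go on.

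If the test sentences govern, there is a second problem. All three named procedures assume that the compared groups are independent. Baseline and follow-up scores from the same patients are not. A test that ignores the pairing uses the wrong variance, so its p-value does not have its nominal meaning. With positive within-patient correlation, the usual result is a test that is too conservative and misses real change. That would be a poor basis for deciding whether to take a pilot treatment further.

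**Working it through.** **1. Setting the two rules side by side.** No arithmetic is needed here.

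| Secondary outcome | General sentence | Outcome's own entry | Agree? |
|---|---|---|---|
| Ultrasound length and lumen | descriptive | descriptive | yes |
| HS Improvement | descriptive | ANOVA, Kruskal-Wallis or rank sum | no |
| NRS pain and stinging | descriptive | individual percentage improvement, no test | yes |
| DLQI | descriptive | ANOVA, Kruskal-Wallis or rank sum | no |

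Two of four entries conflict. Restricting the general sentence to secondary outcomes does not help, since both conflicting entries are secondary. No sentence calls the tests exploratory or exempts these two outcomes.

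**2. What an independent-group test does to paired data.** The plan states no alpha, effect size, SD or correlation, so it has no figure to reproduce. Inputs:

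- n = 20, from Sample Size Justification.
- Assumed: two-sided 0.05, normal scores with equal SD at both visits, complete data, one follow-up visit against baseline, a true shift of 0.5 SD of the raw score for power, and within-patient correlation ρ of 0, 0.3, 0.5 or 0.7.

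The variance of a patient's change is 2σ²(1 − ρ). An independent-group test works as if it were 2σ². As a large-sample guide, its 1.96 cut-off acts like 1.96/√(1 − ρ). At ρ = 0.5 this is 1.96/0.707 = 2.77, which corresponds to a two-sided size of about 0.6%.

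Simulation at n = 20 (20,000 trials per setting; rank sum by normal approximation with continuity correction, signed-rank exact) gives:

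| ρ | Rank sum size | Signed-rank size | Rank sum power | Signed-rank power |
|---|---|---|---|---|
| 0 | 4.9% | 4.9% | 32% | 30% |
| 0.3 | 2.1% | 4.9% | 29% | 41% |
| 0.5 | 0.8% | 4.9% | 27% | 54% |
| 0.7 | 0.2% | 4.9% | 24% | 77% |

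At ρ = 0.5 a paired t-test has about 56% power in the same normal model, so the gain comes from pairing and not from the signed-rank test in particular.

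**3. What estimation alone would offer.** The 95% half-width for a mean change, in SDs of the change, is t(0.975, n − 1)/√n:

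- n = 20: 2.093/√20 = 0.47
- n = 14: 2.160/√14 = 0.58

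At ρ = 0.5 the SD of change is σ√(2 × 0.5) = σ, so with 20 patients the interval is about ±0.47 raw-score SD.

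**The case against.** The strongest reply has four parts.

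- **This is a pilot.** It has no sample size calculation, and the text shows no alpha or decision rule. Nothing visible turns on these p-values, and the tests could be meant as supportive. That limits the seriousness, and it is accepted. But the text does not call the tests supportive, and a pilot label does not tell the analyst which rule to follow.
- **The conflict is narrow.** The general sentence stands under the secondary heading. A reader might infer that the whole plan, primary analysis included, contradicts itself. That holds only if the sentence is taken literally. The certain conflict is HS Improvement and DLQI.
- **The grouping factor is never stated.** A reader might infer that the tests are definitely misapplied. The plan allows one to three injections and records Hurley stage, and comparing such subgroups by ANOVA or Kruskal-Wallis would be legitimate. This stands as a caveat. Comparison by visit is still the likelier reading, because the only comparison the design section describes is with baseline.
- **An improvement rating may have no baseline value, and some patients may have only three visits.** Both are correct, and the fix has to allow for them.

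A reader might also infer that several tests at several visits inflate false positives. The documents do not support a figure for this. They name neither the instruments behind the physician and patient assessments nor an alpha. Positive within-patient correlation also pushes the named tests towards too few rejections.

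**Conclusion.** The internal contradiction is certain. Two of the four secondary outcomes are assigned tests that the section's own general rule excludes, and no available text reconciles them. The conflict extends to the primary parameter only if the descriptive sentence is read literally.

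The mismatch between test and design is likely but not certain, since it depends on the tests being applied across visits. If they are, the error rates are wrong. At an assumed correlation of 0.5, one rank sum test against baseline has a true size of about 0.8% and about 27% power for a 0.5 SD shift, against about 5% and 54% for signed-rank. The gap widens as the correlation rises and vanishes at zero. These figures also rest on normal data and 20 complete pairs.

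A reader might infer that the plan names no primary measure, visit or alpha at all. None appears in the text available to this review, but Appendix 2 and part of the study table were not available, so that remains conditional.

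The point should be corrected before analysis. It is a risk to reporting and interpretation in a non-confirmatory study, not a demonstrated bias in a result.

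**What to change.** Before analysis, make the primary and secondary parameter sections agree.

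- **Preferred, because it fits the pilot aim and the no-power statement:** delete the test sentences for HS Improvement and DLQI. Report change from baseline, or the level at each visit where there is no baseline value, with 95% confidence intervals labelled as not for hypothesis testing. Leave ultrasound descriptive, as the plan already states.
- **If any test is kept, including those for the primary parameter:** label it exploratory, and limit the descriptive sentence to the outcomes it is meant to cover. Replace the choice of three independent-group tests with one paired method named in advance, at a visit named in advance. A Wilcoxon signed-rank or paired t-test of change from baseline would serve, as would a repeated-measures model. The documents do not dictate which measure or visit to name. The measure needs a baseline value, and the choice of visit should allow for patients who attend only three.

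The cost is rewording, with no new visits or data. The wording should be agreed with whoever is responsible for the analysis. The downside is fewer p-values, or none.

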##### Study Table (Chart with Study Procedures)

Activity (timeline)	0 week (Baseline)	2 Week	4 Week	Week 8
Subject Information and Informed Consent	✓			
Eligibility Criteria	✓			
Medical History	✓			
Prior and concomitant therapy	✓			

Review and document pregnancy avoidance with females of child bearing age	✓			
23.4% Hypertonic Saline Injection	✓	✓	✓	
Urine Pregnancy Test (For all females of childbearing age)	✓	✓	✓	
Ultrasound (to locate the tracts)	✓			✓

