#### **B5. POSSIBLE RISKS AND ANALYSIS OF RISK/BENEFIT RATIO**

Hypertonic saline is as effective as other sclerosants with the advantage of lack of allergenicity and low costs. The most common adverse events or risks associated with sclerotherapy using hypertonic saline are hyperpigmentation, teleangiectic matting (neovascularization), pain, ulceration and tissue necrosis. Other reported less common adverse events include exacerbation of hypertension, necrosis of kidney cortex, hemolysis, hematuria, central nervous system disorders, hyponatremia and membranous fat necrosis.

When used to treat fistulas or sinus tracts, none of the systemic adverse events are expected to occur. The common adverse events can be minimized by adhering to meticulous technique.

Risks listed in ICF are as follows:

**More Common:** Stinging, pain in the injected area

**Less Common:** Skin Ulceration,

**Rare:** Infection

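### The only NRS summary named for pain and stinging is a per-patient percentage improvement with no visible reference score, which does not show how painful the injection is

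*Combined protocol and SAP*

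**What the plan says.** B3.A (Study Design and plan) states what the NRS records and when: "Pain and stinging during treatment sessions will be monitored using numeric rating scales (NRS". That sentence has no comparator. An earlier sentence in the same section compares the physician and patient assessments of clinical effect at weeks 2, "week four (t=4) and week 8 (t=8) and compared with the first visit (baseline) (t=0".

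The number of injections varies by patient: "If necessary, subjects will be eligible to receive another hypertonic saline injected in week 2 and/or week 4, with a maximum of three injections". In the Study Table, the row "23.4% Hypertonic Saline Injection" is ticked at weeks 0, 2 and 4 and not at week 8.

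B3.B.a (Sample Size Justification) says: "A sample size calculation is not applicable, for this is an early feasibility and tolerability pilot study". B5 gives, as the only more common risks in the consent form, "Stinging, pain in the injected area".

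Under Secondary study parameter(s) in B3.B.b, the NRS is listed among the patient-reported outcomes as a continuous variable, followed by: "Per individual a percentage improvement will be calculated as a main outcome". The same section opens with a general statement: "Therefore all outcomes will be assessed by using descriptive statistics".

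**The concern.** The NRS is aimed at the effects the consent form treats as most likely. Planners of a later trial will want to know how much the injection hurt, in everyone who received it. A percentage change answers a different question: how far a score moved relative to some starting value.

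The starting value is not identified either. It could be the first injection, the previous injection, or a baseline visit score. Two analysts holding the same scores could therefore report different results, and some injected patients could be left out of the one NRS figure that the plan singles out.

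**Working it through.** The plan states no NRS figure, target or power, so there is nothing to reproduce. The check is arithmetic on the named summary.

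**Inputs.** N = 20 (Sample Size Justification). One to three injections per patient, with repeats only as needed (Study Design and plan). No injection at week 8 (Study Table). The scale range is not in the visible text; whole points from 0 to 10 are assumed. All scores below are illustrative.

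**Formula.** Percentage improvement = 100 × (reference − later) / reference.

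**1. Level of pain.**
- 10 to 8: 100 × 2/10 = 20%. 5 to 4: 100 × 1/5 = 20%.
- 10 to 5, 8 to 4 and 2 to 1 all give 50%.

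The same percentage comes from high and low scores, so the level cannot be recovered from it.

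**2. Zero reference.** With reference 0 the denominator is 0, and no value exists whatever the later score. The section gives no rule for this case.

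**3. Choice of reference.** A later score of 6 gives:
- against 8: 100 × 2/8 = +25%
- against 6: 0%
- against 5: 100 × (−1)/5 = −20%
- against 4: 100 × (−2)/4 = −50%

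**4. Two readings of the text.**

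*Reading A: one session against another.* This follows from the sentence that places the NRS within treatment sessions. A patient injected once has a pain score but no percentage. If 25%, 50% or 75% of the 20 were re-injected (an assumed range; the documents give no rate), then 5, 10 or 15 patients would contribute.

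*Reading B: a visit score against baseline.* This follows from the efficacy wording that introduces the secondary outcomes and from the baseline comparison in B3.A. Patients injected once can contribute. But if the baseline score is the one taken during the week 0 injection, a lower score at week 8 may only reflect that nothing was injected that day.

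| Illustrative patient | Reading A | Week 8 against week 0 injection |
|---|---|---|
| 6 and 4 at two injections, 0 at week 8 | 100 × 2/6 = +33% | 100 × 6/6 = +100% |
| 8 at a single injection, 2 at week 8 | no value | 100 × 6/8 = +75% |

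**5. What a level summary would give.** If all 20 patients have a week 0 session score and the SD is 2 to 3 points (assumed), the 95% half-width for the mean is t(0.975, 19) × SD/√20 = 2.093 × 2/4.472 = 0.94 to 2.093 × 3/4.472 = 1.40 points. Even this small pilot could describe the level usefully.

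**The case against.** The strongest reply is that the general statement on descriptive statistics covers the NRS, that session scores are collected, and that being one main outcome does not exclude other summaries. This stands as far as it goes. A reader might infer that pain levels will go unreported; the documents do not support that. They permit raw scores but commit to no level, maximum or per-session summary, while the percentage is expressly named.

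Second, the tolerability framing rests on the sample size paragraph alone. B1 states the purpose as evaluating the treatment's effect, and the primary parameter is clinical efficacy. If the percentage was meant as an efficacy measure, faulting it for not describing injection pain is partly beside the point. That is fair, and it is why the fix covers both intentions. It does not supply a reference score or remove the zero-reference problem.

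Third, the Study Table appears cut short and Appendix 2 is not shown. A reader might infer that the plan never says when the NRS is taken; that cannot be concluded. Timing given there could narrow the readings, but it would not make a percentage show a level.

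Finally, a reader might infer that percentage change will materially bias the result, because rises and falls are weighted unequally. The documents give no score distribution from which to judge that, so the point does not rely on it.

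**Conclusion.** The concern holds in a limited form. The one NRS summary that the plan names does not show how painful the injection is, has no value at a zero reference, and has no reference score in the visible text. If sessions are compared with each other, it also omits every patient injected once. The number of patients affected cannot be derived from the documents; the counts of 5, 10 or 15 contributors show a range only. The percentages rest on an assumed 0-10 scale, but the loss of level and the zero-denominator problem apply to any scale that starts at 0.

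This should be changed because the plan names a poor main summary where a better one is available from scores already being taken. It is a reporting weakness in a small descriptive pilot and does not bear on the primary efficacy assessment.

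**What to change.** In Secondary study parameter(s), replace the percentage sentence with wording such as:

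> NRS pain and NRS stinging will be summarised separately as raw scores at each injection session (n, median, IQR, maximum) for every injected patient. Absolute within-patient change between sessions will be reported only for patients with two or more injections, with their number.

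If a visit-level comparison with baseline was intended, state the reference score and the time points and use absolute change. Do not use the week 0 injection score as the reference for week 8, when no injection is given. Align the NRS wording in B3.A and B3.B.b accordingly.

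**Cost.** The per-session summary needs no added data collection, because B3.A already has the NRS taken during sessions. It means slightly more descriptive reporting and no single headline percentage. The visit-level alternative is free only if such a score is already collected, and the visible text does not show one; otherwise it would add an assessment.
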